CHOP is a prospective observational cohort study with four tracks ([1] medical professionals, [2] community, [3] employee, and [4] randomized controlled trial [RCT]) to allow results to be compared among the subjects in the four tracks. [1] Current and future medical professionals will be trained in classes within their track in how to educate patients about nutrition, and their results for their DACs will be compared to those who receive traditional clinical education. [2] Adults, adolescents, and children 7 years and older will be offered classes in their community track to allow comparison of their DACs and health metrics with those who do not take the classes. [3] Employees and their families who take the GCCM classes as employee wellness programing will have their DAC and health metrics compared to employees who do not take the classes. And finally, [4] subjects with such chronic health conditions as diabetes will be randomized with equal 50% chance to either taking the GCCM classes or receiving medical nutrition therapy (MNT) with a registered dietician (RD).

DAC surveys will take place for the first track at the beginning and end of each academic year. Surveys will take place for the last three tracks at the first and last class for the treatment (GCCM) class group, and the beginning of the study and 2-3 months later for the control groups (those who do not take the classes). The same adult and children surveys will be used across tracks [2]-[4] for adults 18 years and older and children 7-17 respectively. Medical professionals in [1] will have the same survey.

CHOP unites such analyses as diffusion of innovation (DOI), social network, and simulation-based medical education with deliberate practice (SBME-DP) along with rigorous statistical methods to answer these questions and hopefully benefit society. Results will be strengthened by using self regulation survey with Tulane marketing students to better design the DAC survey based on understanding what DACs predict

Version Date: 09/26/15 Version Number: 1 Page 2 of 9 certain nutrition behavior, in addition to comparison to the de-identified National Health and Nutrition Examination Survey (NHANES) for national trends in diet and similar health metrics and behaviors.

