# 3. Procedure

[1] Medical professionals track: An internet link will be distributed to subjects through the list-serves for each class at the beginning and end of each academic year after they have had the opportunity to participate or not in the voluntary GCCM classes. Residents and practicing physicians who identify themselves through the GCCM website will be subsequently offered the survey. Marketing students will be offered an online survey about self-regulation and nutrition through their marketing class to improve the medical professionals survey.

[2] Community, [3] Employee, and [4] RCT tracks: Subjects in the treatment group will receive up to 20 evidence-based classes (50 hours) of cooking and nutrition education that cover the Mediterranean diet, food shopping, cooking, and storage. Subjects in the control groups for [2] and [3] will not receive the classes, and control subjects in [4] will receive MNT. Control subjects in [2] will additionally have the opportunity to receive either healthy food vouchers for 2 months or have nutrition education for their children before they enroll in the classes in order to compare if increased healthy food access and education compared to GCCM classes best prepares them to benefit from nutrition education. DAC surveys will be used at the beginning and end of the classes for the treatment group, and beginning of the study and 2-3 months later for the control group. Health metrics will be assessed from health records for subjects retrospectively 3 years before and 3 years after their treatment or control exposure, once subjects provide release to the study team of their records with appropriate safeguards to protect

Version Date: 09/26/15 Version Number: 1 Page 3 of 9 the safety of their data. Recruitment for [2] will be through GCCM's website, [3] will be through Laitram that promotes the classes to their employees, and [4] through Tulane University Hospital and Clinic (including the Internal Medicine Practice, Uptown Square clinic, Endocrinology clinic, and Metairie Multispecialty clinic) by study staff. Health metrics will be obtained for [2,4] from Tulane University Hospital and Clinic if subjects' information is stored there, from Marathon Health the third party provider of health care for [3], and from non-Tulane health care institutions for [2,4]. Marathon and non-Tulane facility health information release forms will be provided to subjects as needed at the time of informed consent.

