# **Statistical Analysis Plan**

# **Power Analysis**

The required calculated sample size to achieve 80% power and detect an odds ratio (OR) of at least 1.50 with a two-sided test set at 5% was 263 cases.

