Doubly robust estimation features a dual strategy of outcome regression that also accounts for the likelihood of receiving an exposure or treatment, such as with a PS. Simply using multivariable regression or PS analysis can lead to biased treatment estimates if either model is incorrectly specified. But with doubly robust estimation using both concurrently, only one model must be correctly specified to produce unbiased estimates. Of all the forms of PS analysis (i.e., matching, stratification, weighting, and adjustment), regression that includes the PS as one of the adjusted variables has quantitative evidence as being the top performing PS method. Finally, mixed effects regression further provides a powerful approach to causal inference. This mixed method contains both fixed effects (FE) and random effects (RE) components, with FE having the distinct advantage of controlling even for nonobserved traits by controlling for all time-invariant traits. FE does this by setting each individual subject as his/her own control and thus models within-person effects. Aside from the theoretical advantages, FE has shown quantitative strengths over competing methods. RE was used to control for what FE cannot,

Version Date: 09/26/15 Version Number: 1 Page 8 of 9 namely, time-varying traits at the individual level with repeated observations over time (as students progressed through their medical education). The multilevel aspect was used to account for the hierarchical nature of the data in which medical trainees responded from different medical institutions. Inverse-variance weighted fixed effects (IVWFE) meta-analysis was used to produce a composite estimate across the 25 competency topics.

This triply robust approach can be represented by the following mathematical formula:

$$\Pr(y_{ij} = 1 \mid u_j) = H(x_{ij}\beta + z_{ij}u_j)$$
(1)

for *M* independent clusters conditioned on random effects  $u_j$  for j = 1, ..., M clusters with cluster *j* constituting  $i = 1, ..., n_j$  observations, outcome  $y_{ij}$ , FE covariate  $x_{ij}$ , RE covariate  $z_{ij}$ , and regression coefficient  $\beta$ , all within a logistic regression equation with logistic cumulative distribution function of  $H(\bullet)$ . The PS is utilized as an additional variable in the above model and is represented as

$$e(x_i) = \Pr(z_i = 1 \mid x_i)$$
(2)

in which exposure probability is conditioned on the covariate  $x_i$  observed.

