The competing causal inference methods of instrumental variable and difference in difference analyses were not utilized due to their methodological weaknesses, respectively, of having varying degrees of reliable instrumental variables and having a prevalence of unobserved confounders exerting time-varying effects before and after the exposure/treatment. The above methods of doubly robust PS adjustment in multivariable regression were therefore integrated with multilevel mixed effects to provide a novel triply robust approach to causal inference. Aside from controlling for the likelihood of receiving GCCM education (via the PS) and unobserved time-invariant traits (via FE) and time variant along with intracluster correlation (via RE), this integrative method controlled via regression for age, gender, race, prior nutrition education, special diet, school year, intended specialty, and medical school. This multilevel approach has a Bernoulli conditional distribution of the response given the random effects and logistic cumulative distribution function for the success probability.

All results are reported as fully adjusted ORs. ORs rather than relative risks were calculated due to the complex data source described above and due to the rare disease assumption. Statistical significance was set at a two-tailed *p* value < 0.05. ML analysis was performed in R 3.3.2 (The R Foundation for Statistical Computing, Vienna, Austria). Statistical analysis was performed in STATA 14.2 (STATACorp, College Station, Texas, United States of America). Ethics approval was obtained through the Institutional Review Board (IRB) of Tulane University.

Version Date: 09/26/15 Version Number: 1 Page 9 of 9

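### Track 1: the start-of-year DAC answer is not a listed covariate and the written model has no subject effect, so starting differences can be read partly as a class effect

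*Combined protocol and SAP*

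**What the plan says.** Section 1 of the protocol states that "DAC surveys will take place for the first track at the beginning and end of each academic year". Section 3 (Procedure) sends the survey link at those two times "after they have had the opportunity to participate or not in the voluntary GCCM classes". So exposure in track 1 is self-selected, and a starting DAC answer is scheduled.

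Under Machine Learning and Statistical Analysis, the SAP describes a propensity-adjusted multilevel mixed-effects logistic regression intended for causal inference. Four statements bear on the starting answer:

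- The regression covariates are listed: the method "controlled via regression for age, gender, race, prior nutrition education, special diet, school year, intended specialty, and medical school". That is eight items, and the starting DAC answer is not one of them.
- The PS is defined only generically, by equation (2), "in which exposure probability is conditioned on the covariate" observed. Its covariates are not named.
- Fixed effects are said to use each subject as his or her own control and to remove time-invariant traits. Random effects are said to handle time-varying individual traits, and the multilevel term to handle medical institutions.
- Difference in difference is considered and rejected.

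The Power Analysis sets the scale of interest: "to achieve 80% power and detect an odds ratio (OR) of at least 1.50".

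**The concern.** Students who already care about nutrition, or already feel competent in it, are the likeliest to join a voluntary class and to score well at the end of the year. Their starting DAC answer is the most direct measure of this that the study collects. If the model neither conditions on it nor compares each person with himself or herself, part of the starting difference stays in the class coefficient.

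The SAP intends to draw causal conclusions, and the composite over 25 competency topics does not help. If the starting gap runs the same way across topics, pooling narrows the interval without removing the shared bias.

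**Working it through.** **1. Does equation (1) give own-control protection?** The linear predictor is x_ij·β + z_ij·u_j. β is common to everyone, u_j is a random effect per cluster, and no subject intercept appears. In a mixed model the fixed part is a set of shared coefficients, which is not a within-person fixed effect. The covariate list points the same way: it includes gender and race, whose main effects a within-person model cannot estimate. The text and the equation therefore describe different models.

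**2. Does adding the baseline as an extra pooled row help?** With a wave term and exposure coded from the end of the year, the data form three cells: all subjects at the start, non-takers at the end, and takers at the end. Three parameters fit three cells exactly, so the exposure OR is still takers against non-takers at the end. The baseline row leaves it unchanged.

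**3. The plan's figure.** The only benchmark is the OR of 1.50 with 263 cases. The 263 cannot be uniquely reproduced, because the reference rate, the allocation and the meaning of cases are not given. At 1:1 and two-sided 5%, the minimum is 384 per arm. Values near 263 need unstated inputs, such as 1:3 allocation. Nothing below depends on 263.

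**4. Illustrative size.** The documents give no DAC rates or correlations, so these inputs are assumptions: true class OR 1; 30% exposed; start score X normal with SD 1 and mean d higher in takers; start-to-end correlation r; end outcome = latent end score above 0; no other covariates.

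*Carry-over: the gap acts only through X.* The end gap is r·d, so P(outcome) is 0.5 in non-takers and Φ(r·d) in takers. Spurious OR = Φ(rd)/[1 − Φ(rd)].

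- d = 0.3, r = 0.5: Φ(0.15) = 0.5596, OR 1.27
- d = 0.3, r = 0.7: Φ(0.21) = 0.5832, OR 1.40
- d = 0.5, r = 0.5 and 0.7: Φ(0.25) = 0.5987, OR 1.49; Φ(0.35) = 0.6368, OR 1.75

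Simulation with 400,000 subjects gives 1.256 and 1.385 at d = 0.3, which agrees within simulation error.

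*Stable trait: the full gap is present at both surveys.* Spurious OR = Φ(0.3)/[1 − Φ(0.3)] = 0.6179/0.3821 = 1.62 for any r. Given X, takers still lead by (1 − r)·d on the latent scale (0.15 at r = 0.5, 0.09 at r = 0.7). Baseline adjustment therefore removes only part of the gap.

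| Analysis, d = 0.3, r = 0.5 / 0.7 | Carry-over | Stable trait |
|---|---|---|
| No baseline | 1.26 / 1.39 | 1.62 / 1.62 |
| Baseline as extra row, end-of-year exposure | unchanged | unchanged |
| Dichotomised baseline as covariate | 1.08 / 1.13 | not tabulated |
| Full-scale baseline as covariate | 0.99 / 0.99 | 1.33 / 1.25 |
| Subject fixed effects, two waves | 0.69 to 0.76 | about 1.01 |

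**5. Cross-check on binary answers.** Assume 40% of non-takers are positive at the start and an imbalance OR of 2. Takers then have odds 0.667 × 2 = 1.333, or 57.1%. Assume 30% of starting negatives are positive at the end, with a persistence OR of 6. Starting positives then have odds 0.4286 × 6 = 2.571, or 72%.

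- Non-takers at the end: 0.6 × 0.30 + 0.4 × 0.72 = 0.468
- Takers at the end: 0.429 × 0.30 + 0.571 × 0.72 = 0.540
- OR = (0.540/0.460)/(0.468/0.532) = 1.33

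With starting rates of 30 to 50%, imbalance ORs of 1.5 to 3 and persistence ORs of 3 to 10, the spurious OR runs from 1.11 to 1.75. It reaches 1.50 only at imbalance OR 3 with persistence OR 6 or more.

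**The case against.** The strongest reply is that the SAP already answers this confounder. Stable nutrition-mindedness is a time-invariant trait, and the SAP says fixed effects remove those. If a subject fixed-effects model were fitted to the two waves, the starting answer would enter as the first observation and a stable trait would cancel (OR about 1.01). That holds for the stated intention but not for the model written down. Equation (1) does not define cluster j explicitly. Even if j were the subject, a random intercept assumes independence from exposure, and voluntary enrolment is the reason to doubt that.

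A second reply is that special diet and prior nutrition education are partial proxies, and step 4 omits them. This is fair, and the ORs there do not represent the full planned analysis. The proxies need not suffice, though. In a separate latent-trait simulation at three selection strengths, such proxies plus a PS built on them left ORs of 1.54, 2.22 and 3.12. Adding one baseline answer to model and PS gave 1.42, 1.90 and 2.54.

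Those last figures support a third reply: baseline adjustment is no complete cure. That stands. Subject fixed effects are not a universal remedy either, since under carry-over they err in the other direction (0.69 to 0.76).

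Three stronger readings are tempting but unsupported:

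- That the baseline is excluded from the PS. Its covariates are simply not stated.
- That special diet and prior nutrition education come from the end-of-year survey. No section says which survey supplies them.
- That the same bias affects track 4. That track is randomised.

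**Conclusion.** The point holds as a gap between the stated and the written analysis. The main self-selection confounder is scheduled for measurement, is missing from the listed covariates, and is not shown to be in the PS. The own-control claim is not carried out by equation (1). Starting differences can therefore be read partly as a class effect.

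A reader might infer that any class effect found would be mere self-selection, or that the bias must match the design OR of 1.50. The documents support neither. In the carry-over model at a 0.3 SD gap the spurious OR stays below 1.50, and it reaches about 1.5 only near a 0.5 SD gap. Under a stable trait it is about 1.6 at 0.3 SD. All of these rest on assumed gaps and correlations, without the listed covariates. The return to an OR of about 1.0 holds only if prior differences act wholly through the measured baseline. In each scenario examined, conditioning on the baseline reduced the bias and adding it as a pooled, end-of-year-coded row did not. The change is cheap and worth making.

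**What to change.** For track 1:

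1. Make the end-of-year answer the outcome. Adjust for the same respondent's answer to the same item, on its full response scale, from the survey preceding first class exposure. Include that answer in the PS, and list all PS covariates.
2. Take special diet and prior nutrition education from that same pre-exposure survey, because the classes could change both.
3. Add a two-wave subject fixed-effects (conditional logistic) analysis as sensitivity. The two approaches can err in different directions, so a disagreement is informative.
4. Either drop the own-control claim for equation (1) or fit the subject-level model it describes.
5. Confirm that the start-of-year survey precedes class exposure, which Section 3 leaves unclear. Trainees are surveyed over several years, so a later year's starting answer may already reflect earlier classes.

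Use the first survey in the same way in the non-randomised tracks 2 and 3. In randomised track 4 it serves precision only.

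The cost is SAP wording, since the surveys are already scheduled. Respondents without a pre-exposure survey need imputation or a sensitivity analysis, and one survey item removes only part of the bias if selection is on a stable trait.

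### Results are reported only as odds ratios, partly on a rare-disease assumption that nothing in the documents supports for binary survey outcomes in a prospective cohort

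*Combined protocol and SAP*

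**What the plan says.** The closing paragraph of the SAP section Machine Learning and Statistical Analysis fixes the effect measure: "All results are reported as fully adjusted ORs". It gives two reasons: "ORs rather than relative risks were calculated due to the complex data source described above and due to the rare disease assumption".

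The same section describes the outcome model as a mixed-effects logistic regression: "This multilevel approach has a Bernoulli conditional distribution of the response given the random effects". It adjusts for, among other things, school year, intended specialty and medical school, so it concerns the medical trainees. An inverse-variance "meta-analysis was used to produce a composite estimate across the 25 competency topics".

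Protocol section 1 describes CHOP as a prospective observational cohort with four tracks, and the trainee data as surveys of dietary habits, attitudes and competencies.

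The only sample-size statement is under Power Analysis: 80% power to "detect an odds ratio (OR) of at least 1.50 with a two-sided test set at 5% was 263 cases". Neither document states an outcome rate or what counts as a positive response.

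**The concern.** The rare-disease assumption has one use: it allows an OR to be read as an approximate relative risk. Here there is no disease outcome in the model and no sampling on outcome that would force the use of an OR. Whether a trainee reports a competency or a dietary habit is not rare by nature, and the documents offer no figure to show that it is.

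What is at stake is interpretation. The estimates and tests are unaffected. A reader told that the outcome is rare may take an OR of 1.50 as a 50% relative increase. With no risks reported in either group, that reader could neither correct the reading nor see the absolute change.

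**Working it through.** **Inputs.** From Power Analysis: OR 1.50, 80% power, two-sided 5%, 263 cases. From protocol section 2: a target of 10,000 respondents in the medical professionals track. Control prevalence p0 and the exposed share are not in the documents. Every value used for them below is an assumption.

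**Step 1. Can 263 be reproduced, and does it reveal a prevalence?** With OR 1.50, the exposed-group risk is p1 = 1.5·p0 / (1 − p0 + 1.5·p0). For equal groups, the usual two-proportion formula is

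n per group = [1.960·√(2·p̄(1−p̄)) + 0.842·√(p0(1−p0) + p1(1−p1))]² / (p1 − p0)², with p̄ the mean of p0 and p1.

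For unequal groups the variance terms are weighted by the exposed share. Expected events are the sum over groups of size times risk.

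*263 as subjects, equal groups.* No prevalence fits. The smallest requirement is 384 per group (768 in total), near p0 = 0.43 to 0.45. A rare outcome needs far more: 911 per group at p0 = 0.10 and 1,689 at 0.05.

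*263 as subjects who have the outcome.* Several solutions fit:

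| Exposed share (assumed) | p0 (assumed) | Total N | Events |
|---|---|---|---|
| 50% | 0.05 | 3,378 | 208 |
| 50% | 0.10 | 1,822 | 221 |
| 50% | 0.228 | 984 | 263 |
| 21.5% | 0.05 | about 4,790 | 263 |
| 24.5% | 0.10 | about 2,380 | 263 |
| 20% | 0.02 | 12,011 | 264 |
| 20% | 0.01 | 23,646 | 260 |

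The last two rows exceed the track's 10,000 target. The 5% and 10% rows do not.

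*263 as cases in a case-control design.* Three controls per case with control exposure 0.35 gives 265 cases. Outcome prevalence does not enter this calculation, and the design would conflict with the stated cohort.

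The figure therefore cannot be derived from the stated inputs, and it neither confirms nor contradicts rarity.

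**Step 2. How far can an OR of 1.50 be from the risk ratio?** For a crude two-group OR, RR = OR / (1 − p0 + OR·p0). The overstatement is (1.50 − 1) / (RR − 1).

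| p0 (assumed) | RR | Relative increase | Overstatement if 1.50 is read as RR |
|---|---|---|---|
| 0.05 | 1.5/1.025 = 1.46 | 46% | 1.08-fold |
| 0.10 | 1.5/1.05 = 1.43 | 43% | 1.17-fold |
| 0.40 | 1.5/1.20 = 1.25 | 25% | 2-fold |
| 0.50 | 1.5/1.25 = 1.20 | 20% | 2.5-fold |
| 0.70 | 1.5/1.35 = 1.11 | 11% | 4.5-fold |

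At 5% the approximation is good. At 40% and above it is poor.

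**Step 3. Does the conversion apply to the SAP's own OR?** Only roughly. Equation (1) conditions on the cluster effects u_j, and the OR is adjusted for covariates. ORs are not collapsible, so putting a marginal p0 into the formula does not return the marginal RR. The table shows the order of magnitude and does not predict this study's results.

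**The case against.** **The OR needs no rare-disease argument.** It is a valid measure, the SAP labels it plainly, and a mixed logistic model produces it at any prevalence. Deleting the phrase changes no estimate and no p value. All of this stands. It also means that the rationale does no work except to suggest a risk-ratio reading.

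**The SAP gives a second reason, the complex data source.** Clustering and repeated responses do explain the choice of a mixed logistic model. They do not prevent risks from being standardised from that model.

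**No outcome rate is known, so overstatement is not shown.** This is correct. A strict coding of a positive response could make some outcomes uncommon. The overstatement is conditional on common outcomes and on ORs being read as relative risks.

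**A reader might infer that the SAP's own 263 contradicts rarity,** because 263 events corresponds to a control prevalence of about 23% with equal groups. The documents do not support that inference. Power Analysis states no allocation and does not define cases. Under protocol section 3 the classes are voluntary for trainees, so an equal split cannot be presumed. With about 21.5% to 24.5% exposed, 263 events fits a 5% to 10% outcome equally well.

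**Conclusion.** The concern holds in a conditional form. The rare-disease rationale is unsupported: it is attached to binary survey responses in a cohort, with no outcome rate given. Reporting only ORs leaves readers without any absolute effect.

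The size depends on prevalences that the documents do not give. For a crude OR of 1.50 read as a relative risk, the relative increase is overstated 1.17-fold at an assumed control prevalence of 10% and 4.5-fold at 70%. It would be wrong to say that the ORs will overstate the effect, or that the power statement disproves rarity. The power statement is too incompletely specified to bear on prevalence either way.

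This is a change the SAP should make. It affects how the results can be read and leaves the planned model intact.

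**What to change.** 1. Delete the rare-disease rationale. The choice of a mixed logistic model is sufficient reason to report ORs.
2. Define a positive response for each outcome, and report its prevalence by exposure group.
3. From the same fitted models, report standardised (marginal) risks in each group, the risk difference and the risk ratio, with 95% CIs, beside each adjusted OR.
4. For the 25-topic composite, pool the topic-level risk differences or log risk ratios with their standard errors, alongside the pooled OR.
5. State the baseline rate, the exposed share and the meaning of cases behind the 263.

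No new data are needed and the primary model is unchanged. The cost is 25 standardisations with standard errors and a further pooling step. The headline effect may also look smaller than the OR alone.

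### Twenty-five competency topics fall under one unadjusted 0.05 threshold, with no primary test or multiplicity control, so the family-wise error is well above 5% if each topic is judged by that rule

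*Combined protocol and SAP*

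**What the plan says.** Three statements in the SAP bear on this.

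- **Topics and composite.** Under Machine Learning and Statistical Analysis: "meta-analysis was used to produce a composite estimate across the 25 competency topics". The pooling method is fixed-effect inverse-variance weighting. This is the only mention of the 25 topics.
- **Reporting and threshold.** The same section says "All results are reported as fully adjusted ORs", and then "Statistical significance was set at a two-tailed" p value below 0.05. No exception is made for any outcome or for the composite.
- **Power.** The Power Analysis gives a sample size "with a two-sided test set at 5% was 263 cases", for "80% power and detect an odds ratio (OR) of at least 1.50". The 5% is undivided and no outcome is named.

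The outcome model is a multilevel logistic regression ("This multilevel approach has a Bernoulli conditional distribution of the response given the random effects"), so each topic is a binary outcome with its own odds ratio. Nothing in the available text of the protocol or SAP names a primary endpoint, makes topic claims conditional on the composite, or adjusts for multiple tests. Protocol section 11 is absent from the text read here and cannot be checked.

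**The concern.** An inverse-variance composite over 25 topics cannot be computed without 25 estimates and their variances, so the topic odds ratios will exist. If they are reported and read against the only rule the SAP provides, any topic with p below 0.05 counts as a finding. The 5% then describes the error rate of each single comparison and not that of the set of claims. An isolated topic may be reported as improved by the classes when the result is chance. The SAP presents the regression as a basis for causal inference and does not label the topic results exploratory, so a reader would take such a claim at face value.

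**Working it through.** **The plan's own figure.** The 263 cases cannot be uniquely reproduced, because the SAP gives no baseline rate, exposure prevalence, allocation ratio or clustering allowance. With 1:1 two-sided allocation the smallest requirement at an odds ratio of 1.50 is about 384 per arm (768 in total). Unstated choices do come close: a case-control calculation with 3 controls per case and 35% control exposure gives 265, and 4 per case with 30% exposure gives 261. The figure is therefore not shown to be wrong, and the rest does not depend on it.

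**Inputs.** m = 25 topics and alpha = 0.05 two-sided, both from Machine Learning and Statistical Analysis. The correlation between topic test statistics, rho, is not given, so a range is assumed.

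**Independent topics, no true effect.**

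- P(at least one false positive) = 1 − 0.95^25 = 72.3%
- P(at least two) = 35.8% (binomial, 25 trials at 0.05)
- Expected number = 25 × 0.05 = 1.25, at any correlation

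**Correlated topics.** The same respondents answer all topics, so rho is probably positive. With equally correlated normal statistics,

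FWER = 1 − ∫ [Φ((1.96 − √rho·u)/√(1−rho)) − Φ((−1.96 − √rho·u)/√(1−rho))]^25 φ(u) du.

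**The composite.** The usual inverse-variance standard error treats the 25 estimates as independent. With equal weights and common correlation rho, the true variance is 1 + 24·rho times the nominal one, so the actual type I error at nominal 0.05 is 2·[1 − Φ(1.96/√(1 + 24·rho))].

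| Assumed rho | FWER, 25 topics at 0.05 | Variance ratio 1 + 24·rho | Composite type I error, usual SE |
|---|---|---|---|
| 0 | 72.3% | 1.0 | 5% |
| 0.1 | 70.5% | 3.4 | 29% |
| 0.3 | 60.7% | 8.2 | 49% |
| 0.5 | 46.7% | 13.0 | 59% |
| 0.7 | 31.6% | 17.8 | 64% |

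The FWER falls to 50% at rho of about 0.46, and at rho = 0.8 it is still 24.2%.

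**Effect of adjustment.** A per-topic threshold of 0.05/25 = 0.002 gives a FWER of 4.9% under independence, and 4.4%, 3.5% and 2.3% at rho = 0.3, 0.5 and 0.7. If a topic has 80% power at 0.05, its power at 0.002 is Φ(1.960 + 0.842 − 3.090) = Φ(−0.288), about 39%. Holding 80% would need (3.090 + 0.842)²/(1.960 + 0.842)² = 1.97 times the sample, so 263 would become about 518.

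**The case against.** - **The SAP never says that each topic is tested.** This is correct. The 25 topics appear only as inputs to the composite, and per-topic testing is an inference. It is a reasonable one, because the composite needs the 25 odds ratios and the reporting rule and threshold cover all results. It should still be stated as an inference.

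- **Topics from one survey are correlated, so 72% is too high.** This also stands in part. A reader might infer that at least one false-positive topic is more likely than not. The documents do not support that, because they give no correlation and the probability drops below one half above rho of about 0.46. What survives is that the error is several times the nominal 5% across the whole range examined.

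- **The composite is the real test, so the topics do not matter.** The SAP neither calls it primary nor makes topic claims depend on it. A reader might also infer that naming it primary would settle the matter. It would not, if the usual standard error is kept: at rho of 0.5 and 0.7 the composite's error (59% and 64%) exceeds that of the unadjusted topics (46.7% and 31.6%).

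- **The work is observational and exploratory.** The SAP does not label it so, and it sets a formal threshold. If discovery is the aim, false-discovery-rate control suits it.

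**Conclusion.** The concern holds in a conditional form. The SAP applies one unadjusted two-sided 0.05 threshold to all results, including whatever is reported on 25 topics, and the available text contains no primary test and no multiplicity control. If topics are judged by that rule, the family-wise error when the classes have no effect is 72.3% under independence and 60.7%, 46.7% or 31.6% at assumed equal correlations of 0.3, 0.5 or 0.7, with 1.25 false positives expected throughout.

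These figures rest on three assumptions: topic-by-topic testing, equal correlation, and no true effect on any topic. The composite figures also assume equal weights. The absence of a rule is certain for the text read. The size of the inflation depends on a correlation the documents do not report.

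**What to change.** 1. **Topics.** Report the 25 topic odds ratios with Holm-adjusted p-values, or Benjamini-Hochberg at 5% FDR if discovery is the aim. Call a topic significant only on the adjusted value. Either method uses the 25 p-values the analysis already yields, and Holm needs no assumption about correlation.

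2. **Composite, if it is to be the single primary test at two-sided 0.05.** Say so in the SAP, and replace the usual inverse-variance standard error with one that allows for correlation between topics answered by the same respondents. A bootstrap by respondent that keeps the institution clustering is one way.

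3. **Timing.** The SAP is written in the past tense. If the data have already been analysed, label the composite a post hoc primary, since naming it now would not make it confirmatory. The adjusted topic p-values remain useful either way.

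**Cost.** The topic adjustment takes a sentence or two in the SAP and a few lines of code. Single-topic p-values become less favourable: at the 0.002 threshold, 80% power falls to about 39%. Holm does no worse than that, because only its first step is that strict. The corrected composite standard error needs some further analysis work.
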